9.4.4 Adherence and Retention Analyses

We will calculate the percent of participants that complete the study as well as the average adherence to protocol in each of the two arms based on participant self-report.

CONFIDENTIAL

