4.7.2 Handling of Participant Withdrawals or Termination

If a participant withdraws between the time of consent and biospecimen collection, the participant will be replaced.

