6.1 Study Procedures/Evaluations

6.1.1 Study Specific Procedures

Biospecimen Collection:

- Biospecimens (1.8mL of maternal breast milk, 1.8mL of maternal urine, and 1.8 mL of infant urine) will be collected at one study visit approximately 2-3 months after enrollment. Biospecimen collection will occur either after a routine well-visit or at the participant's home. If a home visit occurs, study staff will go to the participant's home. Refer to Section 6.2 for more details.

Data Collection:

- Participant's electronic medical record will be used to monitor when they have delivered.
- Either the infant's medical record or the NYU CHES study records will be used to obtain birth weight and length for analysis.
- NYC CHES study questionnaire data that participants previously completed under the NYU CHES study will be pulled from the NYU CHES study database.

CONFIDENTIAL

- We will create a new database for the Diaper Study where we will store all Diaper Study-related results along with demographic and NYU CHES study questionnaire data to be pulled from the NYU CHES database.

Questionnaire Administration:

- Participants will be asked to complete a brief adherence questionnaire at three postpartum time points.
 - Questionnaire will be administered over the phone by study personnel 2 weeks and 6 weeks after diaper intervention has begun.
 - Questionnaire will also be administered during the single study visit.
- It will take less than 5 minutes to complete questionnaire.
- Questionnaire responses will be entered into REDCap by study personnel.
- The purpose of the questionnaire is to assess if the diaper delivery service is working smoothly for the mother and to gauge adherence to group assignment.
- Questionnaire data collected from this study will be shared with qualified researchers on the NYU CHES study.

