6.3.6 Withdrawal Visit

- No procedures or evaluations will be done and no biospecimens will be collected if a participant withdraws or is terminated early.

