9.4.5 Baseline Descriptive Statistics

T-tests and chi-square tests (as appropriate) will be used to assess differences in demographic characteristics between participants in the intervention and control groups.

Because this is a pilot analysis, it is not adequately powered to detect statistically significant associations or to permit controlling for covariates or multiple comparisons. The sample size (10 total; 5 per group) has been determined based on budgetary considerations.

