9.4.6 Enrollment/Randomization/Masking Procedures

Participants will be assigned to either the intervention or control group on an alternating basis upon enrollment. Because of the nature of the intervention (cloth vs. conventional diapers), they will not be blinded. If a participant needs to be replaced, the replacement will be assigned to the same group as the participant who withdrew.

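### Adherence by arm (9.4.4) can overstate how well the regimen was sustained, because mothers who leave the study are asked nothing at exit and are replaced within their arm

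*Combined protocol and SAP*

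**What the plan says.** Section 9.4.4 plans two quantities: "We will calculate the percent of participants that complete the study", and the "average adherence to protocol in each of the two arms based on participant self-report". It does not say how reports are combined, which mothers count in either denominator, or how time after exit is treated.

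Section 6.1.1 fixes where self-report comes from: "Questionnaire will be administered over the phone by study personnel 2 weeks and 6 weeks after diaper intervention has begun", and "Questionnaire will also be administered during the single study visit". Section 6.3.5 places that visit 2 to 3 months after the start.

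On leaving, 6.3.6 states: "No procedures or evaluations will be done and no biospecimens will be collected if a participant withdraws or is terminated early". Section 4.7.2 adds: "If a participant withdraws between the time of consent and biospecimen collection, the participant will be replaced". Section 9.4.6 adds that "the replacement will be assigned to the same group as the participant who withdrew".

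**The concern.** Feasibility is the primary objective (2.1), and 9.4.1 attaches no statistical endpoint to it. The two quantities in 9.4.4 are therefore almost all the plan will calculate about whether mothers can sustain the assigned products. Self-reported compliance also defines the per-protocol analysis in 9.3.

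A mother who leaves at week 3 has given at most one report, made while she was still willing to take part. Her remaining ten assigned weeks do not enter the data. Nothing in the plan asks when she stopped using the products, what she used instead, or why. Her replacement can then supply all three reports. If leaving is more common in one arm, the distortion falls mainly on that arm, and the comparison of adherence between arms suffers too. Section 1.2 envisages scaling the protocol up, and the stop date and reason are what a larger trial would need from this pilot.

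**Working it through.** **The plan's own figure.** Arm size is the only one: 5 + 5 = 10, which agrees with 9.4.5. The documents give no adherence level, dropout rate or averaging rule, so there is no adherence figure to reproduce. What follows is illustration.

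**Inputs from the plan.** Five completers per arm once leavers are replaced (9.4.5, 4.7.2, 9.4.6); three assigned months; reports at about weeks 2 and 6 and at the visit (6.1.1); no report at exit (6.3.6).

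**Assumptions.** Three months is 13 weeks. Completers are at 90%. *k* mothers in the arm leave at week 3 and stop use on leaving. Each gave one week-2 report *r*, which describes her use up to exit. Each mother contributes one value.

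**Formulas**
- Leavers' reports kept: A = (5 × 0.90 + k·r) / (5 + k)
- Leavers' reports dropped: D = 0.90
- All assigned time, zero after exit: T = (5 × 0.90 + k·r × 3/13) / (5 + k)

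**Two leavers (k = 2, seven mothers assigned)**

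| r | A | T | A − T |
|---|---|---|---|
| 100% | (4.5 + 2)/7 = 92.9% | (4.5 + 0.462)/7 = 70.9% | 22 points |
| 50% | (4.5 + 1)/7 = 78.6% | (4.5 + 0.231)/7 = 67.6% | 11 points |
| 0% | 4.5/7 = 64.3% | 4.5/7 = 64.3% | 0 |

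**One leaver (k = 1).** At r = 100%: 5.5/6 = 91.7% against (4.5 + 0.231)/6 = 78.8%, 13 points. At r = 50%: 5.0/6 = 83.3% against (4.5 + 0.115)/6 = 76.9%, 6 points. At r = 0%: 75.0% on both counts.

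**Effect of the unstated rule.** If leavers' reports are dropped, the arm shows 90% whatever they said. With two leavers that is 19 points above T at r = 100% (90 − 70.9) and 26 points above at r = 0% (90 − 64.3). If all questionnaires are pooled instead of averaged per mother, there are 5 × 3 + 2 = 17 reports, and r = 0% gives 13.5/17 = 79.4% against 64.3%. The absence of a gap at r = 0% therefore needs the reports kept and one value per mother.

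**Shorter period.** The visit may come at two months. With 9 weeks, r = 100% and k = 2, T = (4.5 + 2 × 3/9)/7 = 73.8%, and the gap is 19 points.

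**A second set of values.** Everyone else is at 80%, and one mother leaves before giving any report and is replaced. The reported mean stays at 80.0%; over all six assigned mothers it is (5 × 80 + 0)/6 = 66.7%.

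**Contrast: she stops the products but stays enrolled.** Four others are at 80%, and she reports 80, 0 and 0, a mean of 26.7%. The arm mean is (4 × 80 + 26.7)/5 = 69.3%, so the loss is visible.

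**The case against.** Several counter-arguments have force.

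- *Giving up the products is not the same as leaving.* A reader might infer that any mother who abandons the regimen disappears from the average. The documents do not support that: one who stays enrolled still answers the later questionnaires and lowers it. The point covers only those who withdraw or are terminated.
- *Upward bias is not certain.* A reader might also infer that the average must be too high. Section 9.4.4 gives no rule, and a leaver who reported poor adherence, with her reports kept, pulls the average down. High reports before quitting are a favourable assumption, and low ones are at least as plausible. Taking 11 to 22 points as the range of the error would be wrong for the same reason.
- *Withdrawal does not establish non-use.* Section 4.7.1 allows withdrawal for any reason and termination on medical grounds or for a newly met exclusion criterion, which under 4.2 includes not breastfeeding. If both leavers in the illustration had gone on using the products fully, the truth would be 6.5/7 = 92.9%, and scoring them zero after exit would give 70.9%, an error of 22 points the other way. This stands, and it rules out zero-scoring as the main figure.
- *Other sections capture the loss.* Section 8 reviews drop-out rates and section 10 requires missing data to be explained. The completion percentage could also show it. But none of these asks for a stop date or reason for stopping the products, and the completion denominator is undefined: one replaced leaver gives 5/6 = 83.3% or 5/5 = 100%. To say that the trial can learn nothing about why the regimen fails would go too far, since the week-2 and week-6 calls ask about delivery and adherence. The survey is a separate attachment and was not available for this review.
- *Feasibility here means recruitment and specimens.* The hypothesis in 9.2 says so, but the primary endpoint in 3.2.1 also requires three months' use of the assigned products. With five per arm, individual reports can be listed, but a listing cannot supply what was never asked.

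**Conclusion.** The point holds for mothers who leave the study. As written, the plan asks them nothing at exit, replaces them within the arm, and leaves open how their earlier reports enter the average. The arm figure can therefore overstate how well the regimen was sustained; it need not.

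The size is conditional. With two leavers at week 3 of 13 who stop use on leaving, completers at 90%, reports kept and one value per mother, the overstatement is about 22 points if they had reported 100%, 11 if 50%, and none if 0%. All these adherence values are assumed. The loss of stop date and reason does not depend on them: it follows from 6.3.6 together with the absence of any other place that asks. This is a cheap improvement to a primary-aim measure and does not invalidate the design.

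**What to change.** 1. **Section 6.3.6.** Allow one voluntary exit item at the contact in which withdrawal or termination is communicated. It would record the last date the assigned products were used, what was used instead, and the main reason for stopping. This changes the present rule, so the wording has to be amended.
2. **Section 9.4.4.** Report adherence for every assigned mother, including those later replaced, with replacements shown separately and beside completion over all assigned mothers. Give adherence while enrolled as the main figure and state how a mother's reports are combined. As a sensitivity figure, give the share of the assigned three months spent on the assigned products, using the reported stop date where known and counting time after exit as non-adherent only where it is unknown.

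The cost is protocol wording and one short optional item in REDCap, with no extra visit or staff. The downside is that reported adherence may be lower and some leavers will decline to answer.

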9.4.5 Baseline Descriptive Statistics

T-tests and chi-square tests (as appropriate) will be used to assess differences in demographic characteristics between participants in the intervention and control groups.

Because this is a pilot analysis, it is not adequately powered to detect statistically significant associations or to permit controlling for covariates or multiple comparisons. The sample size (10 total; 5 per group) has been determined based on budgetary considerations.

9.4.6 Enrollment/Randomization/Masking Procedures

Participants will be assigned to either the intervention or control group on an alternating basis upon enrollment. Because of the nature of the intervention (cloth vs. conventional diapers), they will not be blinded. If a participant needs to be replaced, the replacement will be assigned to the same group as the participant who withdrew.

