Brief Summary	Phthalates and bisphenols have been detected in a range of infant care products. This pilot study will test whether intervening on these sources of exposure during the critical period of minipuberty affects infants' body burden of phthalates and bisphenols. We will recruit 10 participants from the ongoing NYU Children's Health and Development Study (CHES) cohort study who are >=37 weeks gestation or <6 months postpartum, carrying a singleton fetus or with a singleton infant, and intending to breastfeed or breastfeeding. We will randomly assign them to use either conventional baby products or phthalate- and bisphenol-free baby products for the first or next three months of their children's lives. Toward the end of the intervention, we will collect maternal breast milk and infant urine, and assay samples for phthalate metabolite and bisphenol concentrations.
Phase	N/A
Objectives	Aim 1: To assess the feasibility of an intervention designed to reduce infant phthalate and bisphenol exposure Aim 2 (exploratory): To compare urinary phthalate and bisphenol exposure levels in the intervention and non-intervention groups, as well as between mothers and children in the control group.
Methodology	Open-label randomized controlled trial

Endpoint	Participants are enrolled until they have been using the assigned diapers for 3 months, toward the end of which time we will collect maternal breast milk and maternal and infant urine to test for phthalate metabolite and bisphenol concentrations
Study Duration	1 year (allows for 6 months of data collection among 10 participants and 6 months of data analysis).
Participant Duration	3 months
Population	We will recruit 10 participants who are already enrolled in the NYU CHES study at the Brooklyn campus. Eligible participants will be ≥ 37 weeks gestation or < 6 months postpartum, carrying a singleton fetus or with a singleton infant, and intending to breastfeed or breastfeeding.
Study Site	NYULH-Brooklyn
Number of participants	10 participants
Description of Study Intervention/Procedure	Half of the participants will be randomly assigned to the intervention group and will receive a three-month supply of phthalate- and bisphenol-free baby products (e.g., wipes, diaper cream) and a subscription to a cloth diaper service.

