3.1 Description of Study Design

- This is a single-site pilot intervention study to be conducted at NYU Langone Health-Brooklyn.
- Participants will be recruited from the ongoing pregnancy/birth cohort study, NYU CHES study.
- Participants will be randomly assigned to an intervention group (N=5) or a control group (N=5).
- Participants will receive a 3-month supply of either disposable diapers and conventional baby products (control group) or cloth diapers and phthalate- and bisphenol-free baby products (intervention group) at no cost.
- Participants will complete brief adherence surveys at three postnatal time points.
- After 3 months, study personnel will conduct a study visit during which maternal breast milk and maternal and infant urine will be collected.
- Urine and breast milk samples will be analyzed for phthalate metabolites and bisphenols in the NYU Human and Environmental Exposure Assessment Facility Core lab.

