6.3.2 Enrollment/Baseline

- Diaper Study team member will obtain consent.
- Diaper Study team member will assign participant to study group in alternating fashion. Participants will not be told of their group assignment in advance of delivery or postpartum consent.
- Diaper Study team member will obtain participant's delivery date from participant's EMR and schedule diaper delivery to their home to begin directly afterward or schedule diaper delivery to begin immediately if consent occurs postpartum.

CONFIDENTIAL

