9.1 Statistical and Analytical Plans

There will not be a formal SAP in this study, as it is a pilot with only 10 participants. Demographics will be compared between members of the intervention and control groups to assess the success of the randomization process. T-tests will be used to compare phthalate metabolite and bisphenol levels between the two groups and correlations of chemical levels will be run comparing mothers and infants in the control group.

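### The study is described as randomized, but its operative procedure is alternation by the recruiting team, so at least 9 of 10 assignments are known in advance and the between-arm comparisons are open to selection bias

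*Combined protocol and SAP*

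**What the plan says.** **Label.** The Protocol Summary gives the methodology as "Open-label randomized controlled trial". Its descriptions of the intervention and reference groups, and Sections 2.1 and 3.1, all speak of random assignment, with five participants in each group.

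**Procedure.** Only two places say how assignment is done. Section 6.3.2: "Diaper Study team member will assign participant to study group in alternating fashion". Section 9.4.6: "Participants will be assigned to either the intervention or control group on an alternating basis upon enrollment".

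**Replacement.** Section 4.7.2: "If a participant withdraws between the time of consent and biospecimen collection, the participant will be replaced". Section 9.4.6: "If a participant needs to be replaced, the replacement will be assigned to the same group as the participant who withdrew".

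**Who does what.** Diaper Study personnel find candidates in the cohort database and screen them (Sections 4.4 and 6.3.1). A Diaper Study team member obtains consent and assigns the group (Section 6.3.2). The only concealment described is that mothers are not told their arm before delivery or postpartum consent.

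**Reliance on randomization.** Section 9.1: "Demographics will be compared between members of the intervention and control groups to assess the success of the randomization process". Section 9.4.5: "T-tests and chi-square tests (as appropriate) will be used to assess differences in demographic characteristics between participants in the intervention and control groups".

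**The concern.** The two procedural sections agree with each other and contradict the label, so this is not a slip in one paragraph. Withholding the arm from the mother limits self-selection at consent. It does not stop staff from knowing which arm the next enrollee will enter.

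Staff also have latitude over whom to contact and when, because eligibility runs from 37 weeks of gestation to 6 months postpartum (Section 4.1). A mother who seems likely to cope with cloth diapers could be enrolled a little earlier or later, without any intent to bias.

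Two outputs are exposed. One is the comparison of infant chemical levels, which Section 9.4.2 uses to assess effectiveness. The other is completion and adherence, with adherence averaged by arm (Section 9.4.4). Laboratory measurement limits bias in assessing the outcome, but not bias in who enters each arm. Section 9.4.5 rules out covariate adjustment as a remedy. Section 2.1 also frames the feasibility question around randomly assigning participants, which alternation does not try out.

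**Working it through.** **Inputs.** 10 participants, 5 per arm (Sections 3.1 and 9.4.5); alternation (6.3.2, 9.4.6); same-group replacement (9.4.6). The sample size was set by budget, so there is no power calculation to reproduce.

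**1. The plan's own figure.** Alternating 10 participants gives 5 and 5, as stated.

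**2. Predictability under alternation.** Only 2 sequences are possible.
- If the first arm is unknown, 9 of 10 assignments are certain. Expected correct guesses = 0.5 + 9 = 9.5 of 10 (95%).
- If the starting arm is fixed, all 10 are certain.

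**3. Predictability under a concealed random 5:5 list.** There are C(10,5) = 252 sequences. For a guesser who sees all past assignments:
- Expected correct guesses = 5 + (2^10/252 − 1)/2 = 5 + (4.063 − 1)/2 = 6.53 of 10 (65%).
- Expected number of certain assignments (entries left after one arm is full) = 2 × 5/(5 + 1) = 1.67.

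**4. Replacements.** Each one's arm is known before recruitment. With d replacements, the share of all assignments that is certain is (9 + d)/(10 + d):

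| d | Certain |
|---|---|
| 1 | 10/11 = 91% |
| 2 | 11/12 = 92% |
| 3 | 12/13 = 92% |

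**5. What steering could do (illustration only).** The documents give no steering size. Assume staff shift the expected outcome of enrollees by +η SD when they expect one arm and −η SD when they expect the other. With p the proportion of correct guesses, expected bias = [10p − 10(1 − p)]η/5 = 2η(2p − 1).

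| η (assumed) | Alternation, p = 0.95 | Random list, p = 0.653 |
|---|---|---|
| 0.10 | 0.18 SD | 0.06 SD |
| 0.25 | 0.45 SD | 0.15 SD |
| 0.50 | 0.90 SD | 0.31 SD |

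With no steering (η = 0) the bias is zero under both. The verdict does not rest on this table.

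**6. Can the baseline tests give reassurance?** For a two-sided 5% t-test with 5 v 5 and a true 1-SD imbalance, the noncentrality is 1/√(1/5 + 1/5) = 1.58 on 8 degrees of freedom, with critical value 2.306. Power is 0.286, about 29%. An imbalance of that size would be missed about 71% of the time.

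**The case against.** **This is a feasibility pilot.** Section 9.4.1 says there are no relevant statistical endpoints for the primary aim. The primary endpoint (Section 3.2.1) is all 10 participants completing and providing specimens. The group comparison is labelled exploratory and stated to be underpowered. This stands, and it limits the damage: a reader might infer that alternation invalidates the feasibility result, but it has little effect on counts of mothers recruited and samples collected. It does not rescue the label or the between-arm figures.

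**Staff may not know the arm when they approach a mother.** Assignment comes at enrollment, after consent. Remote candidates review the materials and call back (Section 4.4). With several candidates pending, their order of consenting settles who takes which slot. This also stands. A reader might infer certainty before every approach, but the documents support certainty only about the next person to enroll. Nor do they say that one individual screens, consents and assigns; they name one team.

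**No bias is shown.** Correct. A reader might infer that selection took place, but the documents describe only a procedure that permits it.

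**The baseline tests are not worthless.** A reader might infer that they cannot detect any selection; 29% power at 1 SD is weak but not zero. Nor is the chi-square test always badly sized. If 3 (or 7) of the 10 share a trait, the uncorrected test rejects when all three (of the smaller category) fall in one arm: 2 × C(5,3)/C(10,3) = 20/120 = 16.7%. That is the worst case, at 2 of 9 possible totals. Size is 4.8% at 4 or 6, 0.8% at 5, and 0 at 1, 2, 8 and 9. Describing the groups is, if anything, more useful when allocation is not random. What fails is treating the comparison as a verdict on randomization.

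**Same-group replacement keeps the budgeted 5:5.** True. That is a reason to allow it with disclosure.

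**Conclusion.** The point holds. The study is called randomized, but the only procedure given is alternation by the recruiting team, with nothing concealing the next arm from staff. At least 9 of 10 assignments and every replacement are known in advance: 9.5 of 10 expected correct guesses, against 6.53 under a concealed 5:5 list. These counts assume that staff know past assignments and that alternation is followed strictly. They describe the moment of enrollment and not every first approach.

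The consequence is an opening for selection bias in the exploratory infant comparison and in adherence by arm. Its actual size cannot be derived from the documents. A study run under Sections 6.3.2 and 9.4.6 as written could not accurately be reported as randomized, so the text needs correcting even though the comparison is exploratory.

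**What to change.** **Allocation (Sections 6.3.2 and 9.4.6).** Replace alternation with a computer-generated 5:5 permuted list of 10, loaded in the REDCap system the study already uses and prepared by an existing team member who does not recruit. Reveal each assignment only after consent and eligibility are recorded. Avoid blocks of two: with known block size they allow 5 × 1.5 = 7.5 of 10 correct guesses, and 5 assignments are certain.

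**Replacements.** Choose one and state it:
- Give each replacement the next concealed entry and accept that group sizes may depart from 5:5. One replacement may give 6:4. With two withdrawals from the same arm and independent 50:50 reserve entries, 7:3 has probability 0.5 × 0.5 = 25%. The fixed group sizes in Sections 3.1, 5.1 and 9.4.5 would need matching edits. This restores unpredictability but does not by itself remove bias from who withdraws.
- Keep same-group replacement and disclose that those assignments are predictable.

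**If alternation is kept or has already been used.** Describe the study as alternately allocated (quasi-randomized) in the Protocol Summary, Sections 2.1, 3.1 and 9.1, and all reports. The study title as given in the Protocol Summary does not use the word and needs no change.

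**Baseline comparison (Section 9.1).** Present it as a description of the groups by arm, not as a test of whether randomization succeeded.

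**Cost.** One protocol amendment touching these sections and, if randomizing, a short list in REDCap. No extra participants or visits. The list must be in place before enrollment starts; for participants already allocated by alternation, only relabelling remains.

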1.1 Background Information and Relevant Literature

In keeping with David Barker's fetal programming hypothesis,¹ studies of associations of phthalates and bisphenols with child health outcomes have focused on *in utero* exposure. Results have been inconclusive, however,^{2,3} with inconsistencies commonly attributed to varying approaches to exposure assessment and other methodological issues. An alternative explanation that has not been explored is the possibility that pregnancy may not be the only—or even the primary—critical period for early-life endocrine disruption. Minipuberty, a brief window during the first six months of life when sex hormones surge in sync with gonadal cell proliferation, may be a particularly vulnerable period for dysregulation of the hypothalamic-pituitary-gonadal axis by endocrine-disrupting chemicals (EDCs).⁴ Because of their estrogenic and anti-androgenic properties, bisphenols and phthalates have the potential to adversely affect the development of reproductive tissue responsible for sex hormone production, with downstream consequences for child health in multiple domains.

While most conceptual models linking EDCs to reproductive health outcomes have focused on prenatal exposure, including Niels Skakkebaek's Testicular Dysgenesis Syndrome theory⁵ and Germaine Buck-Louis's companion Ovarian Dysgenesis Syndrome theory,⁶ gestation is not the only critical period in the development of reproductive endocrine glands. Testicular Leydig and ovarian granulosa cells undergo three phases of maturation, culminating in sexual maturity. The first is mid-pregnancy, when Leydig cells proliferate in the fetal testis⁷ and primordial follicles emerge in the fetal ovary.⁸ The second is during minipuberty, when Leydig cells undergo another burst of proliferation and differentiation, and granulosa cells also proliferate as part of the postnatal surge in folliculogenesis.⁹ Finally, both become fully activated in puberty. During minipuberty, reproductive hormone concentrations rise precipitously, peaking between two and three months postnatally,⁴ only to become quiescent after about six months of age until reactivated during puberty. Disruption of this intricate choreography by exposure to EDCs could have negative consequences for the development of a variety of tissues and organs that are regulated by sex hormones, including brain, bone, adipocytes, and gonads.

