4.1 Inclusion Criteria

In order to be eligible to participate in this study, an individual must meet all of the following criteria:

1. Enrolled in NYU CHES study at the NYULH-Brooklyn campus
2. Over 18 years of age
3. At least 37 weeks gestation or <6 months postpartum
4. Carrying singleton fetus or having given birth to a singleton infant
5. Intending to breastfeed or breastfeeding
6. English or Spanish speaking
7. Intending to obtain/obtaining pediatric care for infant at the Sunset Park Family Health Center at NYU Langone

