4.5 Duration of Study Participation

The estimated time of enrollment is 1-3 weeks prior to delivery or within 6 months postpartum. Participants and their infants will be enrolled for three months.

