6.3.5 Study Visit

- After using products in assigned study group for up to three months, a single study visit will occur after a routine well-visit or at participant's home between 2 and 3 months after diaper intervention has begun. If visit cannot occur after infant's well-visit, Diaper Study team member will go to participant's home.
- Diaper Study team member will confirm consent.
- Participants will be asked to provide maternal breast milk and urine samples.
- Diaper Study team member will collect infant urine sample.
- Participants will complete questionnaire.

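### A single alternating sequence covers both prenatal and postpartum entrants, so infant age at sampling may differ between arms of 5; separate lists by entry route would reduce this at little cost but not remove it.

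*Combined protocol and SAP*

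**What the plan says.** Section 4.1 admits women by either of two routes: "At least 37 weeks gestation or <6 months postpartum". Section 4.5 repeats this: "The estimated time of enrollment is 1-3 weeks prior to delivery or within 6 months postpartum".

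Section 9.4.6 assigns all of them by one rule: "Participants will be assigned to either the intervention or control group on an alternating basis upon enrollment". Section 6.3.2 agrees: "Diaper Study team member will assign participant to study group in alternating fashion". Neither section separates the routes. A replacement takes the arm of the woman who withdrew, with no condition on entry route (9.4.6).

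Products start directly after delivery for prenatal entrants. For the others, staff "schedule diaper delivery to begin immediately if consent occurs postpartum" (6.3.2). The visit at which urine and milk are collected falls "between 2 and 3 months after diaper intervention has begun" (6.3.5). Section 6.1.1 uses a different clock: samples "will be collected at one study visit approximately 2-3 months after enrollment".

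The infant comparison is by t-test (9.1, 9.4.2). Section 9.4.5 says the sample does not permit control for covariates. The baseline comparison covers demographics; infant age at product start or at sampling is not named.

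**The concern.** Infant age at sampling depends on when the mother joined. The protocol itself treats age as important: section 1.1 says reproductive hormones peak at two to three months and then fall, "only to become quiescent after about six months of age until reactivated during puberty". Section 1.2 links exposure to features of infant skin and body proportions. An arm with more late entrants would therefore differ from the other in infant age as well as in assigned products.

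With 5 infants per arm, one or two placements move the mean noticeably. Nothing later in the plan would correct this, because the t-tests are unadjusted, and nothing requires age by arm to be reported. The infant comparison is the study's only look at whether the products change exposure, and section 1.2 says the protocol may be scaled up if successful.

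**Working it through.** The plan has no calculated figure to reproduce. Ten participants, 5 per arm, is a budget figure (9.4.5), and alternation of 10 does give 5:5.

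**Age at sampling** (4.1, 6.3.2, 6.3.5) is age at product start plus 2 to 3 months.
- Prenatal route: 0 + 2 to 0 + 3, so about 2 to 3 months.
- Postpartum route: 0 + 2 up to <6 + 3, so about 2 to just under 9 months.
- On the 6.1.1 clock, a woman enrolled 3 weeks before delivery could have her infant sampled at roughly 2 − 0.7 = 1.3 months.

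**Balance of entry route under one sequence.** Let k of the 10 enter prenatally. The documents do not give k, so a range is shown. Assume random entry order. The number x of prenatal entrants in one arm then has probability C(k,x)·C(10−k,5−x)/C(10,5), with C(10,5) = 252.
- k = 5, split 4:1 or worse: (1 + 25 + 25 + 1)/252 = 52/252 = 20.6%.
- k = 4, split 3:1 or worse: (6 + 60 + 60 + 6)/252 = 132/252 = 52.4%.

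The values jump between odd and even k because an even k allows a difference of exactly 2, while an odd k goes from 1 to 3.

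**Shift in mean entry age at a 4:1 split (k = 5).** One arm has 1 postpartum infant and the other has 4. Prenatal entry counts as age 0.
- Postpartum entry uniform over 0 to 6 months (assumed, mean 3): (4 × 3)/5 − (1 × 3)/5 = 2.4 − 0.6 = 1.8 months on average.
- Maximum: the four at 6 months and the single one at 0, giving (4 × 6)/5 − 0 = 4.8 months.

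**Effect of separate lists.** A simulation of 200,000 runs assumed postpartum entry uniform over 0 to 6 months and sampling uniform 2 to 3 months after start. The lists by route keep arms at 5:5 and prenatal counts within 1.

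| Prenatal entrants of 10 | Counts differ by ≥2, one sequence | Mean ages differ >1 month, one sequence | Mean ages differ >1 month, lists by route |
|---|---|---|---|
| 2 | 44.4% | 44% | 32% |
| 3 | 16.7% | 45% | 38% |
| 4 | 52.4% | 45% | 26% |
| 5 | 20.6% | 44% | 33% |
| 6 | 52.4% | 42% | 17% |
| 7 | 16.7% | 37% | 27% |
| 8 | 44.4% | 31% | 5% |

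For a gap above 2 months, the probability falls from 12.7% to 1.9% with k = 4, and from 11.7% to 4.0% with k = 5. With k = 0 there is no gain: 37% either way for a gap above 1 month.

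**Worst case that remains.** With k = 5 and lists by route, one arm can hold 3 postpartum infants near 6 months while the other holds 2 near 0: (3 × 6)/5 = 3.6 months. Under one sequence, a 5:0 split allows (5 × 6)/5 = 6.0 months.

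**The case against.** The strongest reply is that entry route is a weak stand-in for age. A woman who joins one week after delivery has her infant sampled at almost the same age as a prenatal entrant's. Anyone joining by about 3 months postpartum is sampled by about 6 months of age. This stands. A reader might infer that allocating within route would prevent uneven ages, or that route decides whether sampling falls within minipuberty. The documents support neither, because postpartum entrants still range from 0 to just under 6 months at product start.

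The probabilities also depend on random arrival. Alternation balances any unbroken run of same-route entrants to within one, so clustered entry would do better than the table suggests. Entry that happened to alternate by route would do much worse. The 52% figure is the highest in the range; 3 or 7 prenatal entrants give 17%.

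A reader might also infer that an age imbalance would create or hide a product effect of known size. The documents give no relation between age and creatinine-adjusted concentrations, so the consequence can be stated only in months of age. Nor do they record what postpartum entrants used before joining; section 1.3.1 says only that conventional products are the US standard.

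Finally, Aim 2 is exploratory, the plan says it is underpowered, and the primary aim is feasibility. That limits the importance of the point but does not remove the case for an inexpensive improvement.

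**Conclusion.** The point holds as a minor design improvement. One unstratified sequence covers two entry routes whose infants are sampled at about 2 to 3 months and about 2 to just under 9 months, and the planned analysis does not correct for any imbalance. Across 2 to 8 prenatal entrants, the chance of prenatal counts differing by 2 or more is 17% to 52%, assuming random entry order.

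Lists by route bring that chance to zero. They only partly reduce the age imbalance: the chance of a gap above 1 month falls from 44% to 33% with 5 prenatal entrants and from 45% to 26% with 4, under the uniform-entry assumption. If all ten enter postpartum, nothing is gained. The feasibility aim is unaffected.

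**What to change.** In 9.4.6, mirrored in 6.3.2:
- Replace the single alternating sequence with two concealed, randomly ordered lists in pairs, one for prenatal and one for postpartum entrants, capped at 5 per arm overall.
- Match replacements on entry route as well as arm; otherwise a replacement can undo the balance.
- Report infant age at sampling by arm. This is useful whatever the route mix turns out to be.

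The cost is one extra list and a few sentences, with no added participants, visits or assays. There are two drawbacks. The second assignment in each pair is predictable, although under alternation every assignment is. The last assignment may be forced by the cap. Random order within pairs is also closer to the random assignment described in the Protocol Summary and section 3.1.

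Two related inconsistencies should be reconciled at the same time: section 2.1 describes product use from birth to 3 months of age while 4.1 and 4.5 allow entry up to 6 months postpartum, and 6.1.1 and 6.3.5 time the sampling visit from different starting points.
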